6.7 Product Handling and Accountability

A system that allows tracking of orders, shipping and returns will be used to control the Vivaer ARC Stylus inventory. The devices will be packaged and labeled to clearly indicate that they are for clinical study use only and must only be used for participants enrolled in this study. All devices not used must be returned to the sponsor disposed of in accordance with the sponsor's instructions. The investigator is responsible for adequate record keeping regarding the receipt, use, and final disposition of study inventory.

7.0 Statistical Considerations

7.1 Study Design

This is a prospective, multicenter, open-label, single-arm study to assess the Vivaer procedure for treatment of SSB to improve symptoms in those diagnosed with NAO. This study is designed to assess improvement in symptoms from prior to the procedure to a primary endpoint at 3 months after the procedure and out to 36 months.

7.2 Study Hypotheses

The primary endpoint hypothesis for the primary study objective is designed to demonstrate that the mean improvement in participant NOSE Scale score from the baseline assessment at screening to 13 weeks exceeds 25 points. Note that improvement is represented by a decrease in NOSE score. The null hypothesis (H_0) is that the decrease in mean NOSE Scale score will be less than 25 points and the alternative hypotheses (H_1) is that the decrease will be more than 25 points:

$$H_0: \mu_d \geq -25.0$$

$$H_1: \mu_d < -25.0,$$

where μ_d represents the mean change in NOSE Scale score from baseline to 13 weeks (13-week NOSE Scale score – baseline NOSE Scale score). Rejection of the null hypothesis in favor of the alternative hypothesis (H_1) means that there is evidence for a statistically significant reduction in mean NOSE Scale score from baseline to 13 weeks postprocedure.

The secondary endpoint hypothesis for the primary study objective is designed to show that the proportion (percent) of participants meeting the responder definition will exceed 0.55 (55%) at 13 weeks. The null hypothesis (H_0) is that the proportion of responders will be equal to .55 (55%) and the alternative hypotheses (H_1) is that the proportion of responders will exceed 0.55 (55%):

$$H_0: p_0 = 0.55$$

$$H_1: p > 0.55,$$

where p_0 represents the targeted minimum responder proportion at 13 weeks and p represents the expected proportion at 13 weeks.

7.3 Power Analysis and Sample Size Estimate

The study will enroll up to 70 participants. The power analysis was performed such that there is adequate power to reject the null hypothesis for both the primary effectiveness endpoint and for the principal secondary endpoint.

The statistical power ($1 - \beta$) for the primary effectiveness endpoint that, on average, there is at least a 25-point improvement in the NOSE Scale score from the pretreatment assessment to the assessment at 13 weeks:

Statistical Hypothesis: $H_0: \mu_d \geq -25.0$ versus $H_1: \mu_d < -25.0$

where μ_d is the average change from screening (baseline) in the NOSE Scale score at 13 weeks post treatment

Statistical Methodology: Single-sample paired t-test

Expected μ_d : -50

Standard Deviation: 20

Significance Level: One-sided $\alpha = .025$

Clinical Study Protocol – SWELL Study

Minimum Sample Size: 70 Participants

Statistical Power: 0.99

The statistical power ($1 - \beta$) for the secondary endpoint is such that at least 55% of the treated participants respond to treatment, defined as either at least one NOSE Scale class improvement, or at least a 20% improvement in the NOSE Scale score, both assessed at 13 weeks posttreatment:

Statistical Hypothesis: $H_0: \pi \leq 0.55$ versus $H_1: \pi > 0.55$

where π is the proportion of participants responding to treatment 13 weeks posttreatment

Statistical Methodology: Single-sample chi-square test

Expected π : 0.80

Significance Level: One-sided $\alpha = .025$

Minimum Sample Size: 70 Participants

Statistical Power: 0.99

With at least 70 treated participants, we can be 95% confident that we will observe at least one unexpected serious device-related event when the underlying incidence of that event is at least 2.3%.

It is anticipated that participants will be enrolled at sites on a competitive basis; however, a reasonable balance of participants among sites may be maintained by potentially capping enrollment at individual sites based on the final number of participating sites.

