7.14 Safety Analysis

All adverse events, collected from the time of study consent (study entry) until the end of the study will be analyzed for all participants. Adverse events may occur during the treatment phase or during the follow-up phase. AEs occurring after the screening assessment but before the procedure (application of anesthesia) will be

Clinical Study Protocol – SWELL Study

documented in the participant's medical record and EDC but will not count as related to the study device or procedure. Adverse events will be coded using a custom Aerin Medical dictionary so that adverse events may be categorized for analysis at an appropriate level of detail. Listings will be provided to detail individual events. The number of participants, number of AEs, and the proportion of participants reporting each AE will be summarized. Seriousness and severity of AEs and their relationship to the device and procedure will be summarized. A time course of adverse events will be presented. Any unexpected adverse device experiences or adverse events that occur at an unexpectedly high incidence rate will receive detailed analyses. Narratives will be presented for all deaths, serious adverse events, unexpected adverse device experiences, and participants withdrawn due to an adverse event.

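### Section 7.3 overstates safety detection: 70 treated participants give 95% probability of seeing at least one event only at an incidence of about 4.2%, not 2.3%

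*Combined protocol and SAP*

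**What the plan says.** Section 7.3 sets the sample size at 70 from two efficacy calculations, for mean NOSE change and for responder proportion. It then adds one safety statement, conditional on treating 70 or more: "95% confident that we will observe at least one unexpected serious device-related event when the underlying incidence of that event is at least 2.3" (percent). No formula or other input is given for that figure.

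The same section opens with "The study will enroll up to 70 participants", and the Protocol Summary gives the same limit. Section 5.3 counts a participant as enrolled once anesthetic is introduced for the study procedure, so the number treated cannot exceed the number enrolled.

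Serious device- and procedure-related events through 3 months, including septal perforation, are a secondary endpoint (Protocol Summary and Section 4.1). Section 7.2 sets no hypothesis or threshold for them. Section 7.11 plans proportions with 95% confidence intervals. Section 7.14 takes the participant as the unit for adverse events: "the proportion of participants reporting each AE will be summarized".

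**The concern.** The rule of three is enough to raise doubt. The incidence at which at least one event is 95% likely is roughly 3/n, and 3/70 is 4.3%, nearly twice the stated 2.3%. Put another way, at 2.3% the expected number of participants with an event is 70 × 0.023 = 1.61, and about 3 expected events are needed before a zero count becomes as unlikely as 5%.

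The safety endpoint has no test and no performance threshold, so this sentence is the only place where the plan says in advance what 70 participants can reveal about rare serious harm. A reader who accepts it could take a study with no such event as good evidence against rates of 2.3% and above. In fact a rate of 2.3% would go unseen in about one study in five. The error runs in the direction favourable to the device.

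**Working it through.** **Inputs, all from Section 7.3**

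- Treated participants: n = 70, which is also the enrolment limit.
- Probability of observing at least one event: 0.95.
- Stated incidence: p = 0.023.

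**Step 1. Try to reproduce the stated figure.** For independent participants, each with event probability p,

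P(at least one) = 1 − (1 − p)^n

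1 − (1 − 0.023)^70 = 1 − 0.977^70 = 1 − 0.196 = 0.804

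The result is 80.4%, which is 14.6 percentage points below the stated 95%. The probability of no event is 19.6%.

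**Step 2. Solve for the incidence that gives 95% with 70 participants.**

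p = 1 − (1 − 0.95)^(1/n) = 1 − 0.05^(1/70) = 0.0419, or 4.19%

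Check after rounding: 1 − (1 − 0.042)^70 = 0.950. The ratio to the stated figure is 4.19 / 2.3 = 1.8.

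**Step 3. Solve for the sample size that supports 2.3% at 95%.**

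n = ln(0.05) / ln(1 − 0.023) = 128.7, so 129 participants

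**Step 4. Look for another convention that would give 2.3%.**

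| Method | Units | Probability | Detectable incidence |
|---|---|---|---|
| Exact binomial | 70 participants | 95% | 4.19% |
| Poisson, −ln(0.05)/n | 70 participants | 95% | 4.28% |
| Rule of three, 3/n | 70 participants | 95% | 4.29% |
| Exact binomial | 70 participants | 97.5% | 5.1% |
| Exact binomial | 70 participants | 90% | 3.2% |
| Exact binomial | 70 participants | 80% | 2.27% |
| Poisson | 70 participants | 80% | 2.30% |
| Exact binomial | 140 nostrils, taken as independent | 95% | 2.1% |

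Every 95% calculation for 70 participants falls between 4.2% and 4.3%. Counting nostrils does not give 2.3% either, and both the sentence and Section 7.14 count participants. The stated figure fits 80% probability with 70 participants, or 95% with about 129. The plan does not say which, if either, lies behind it.

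**Step 5. Sensitivity to a shortfall.** The plan gives no expected shortfall, so these cases are illustrative assumptions. With 63 treated, the incidence detectable at 95% is 1 − 0.05^(1/63) = 4.6%. With 60 treated it is 1 − 0.05^(1/60) = 4.9%.

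**The case against.** The strongest reply is that the sentence decides nothing. The sample size rests on the two efficacy hypotheses, study success in Section 5.5.2 depends only on mean NOSE change, and the stopping reasons in Section 9.4 use no incidence threshold. Correcting the figure changes no test, endpoint or population. This is true, and it limits the reach of the error.

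A second reply is that Section 7.11 already plans 95% confidence intervals for septal perforation and for the serious related events. With 0 of 70 events the exact two-sided upper limit would be 1 − 0.025^(1/70) = 5.1%, so the report itself would show that rates well above 2.3% remain possible. This reduces the risk of a wrong final conclusion. It does not correct a statement that readers of the protocol rely on before there are data, and it would leave the report at odds with Section 7.3.

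A third reply is that 70 may not be a ceiling, since Section 7.3 also labels 70 a minimum sample size and speaks of at least 70 treated. That inconsistency is real, but it does not rescue the figure: the plan nowhere provides for anything near 129 participants. Nor does dropout after treatment reduce the number treated. Only under-recruitment, or a procedure abandoned after anesthesia, would do so, which is why the 63 and 60 cases are illustrations only.

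None of these replies disputes the arithmetic.

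**Conclusion.** The statement in Section 7.3 is wrong as written. With 70 treated participants, 95% probability of seeing at least one event requires a true incidence of about 4.2%. At the stated 2.3% the probability is 80.4%, and the chance of missing the event altogether is 19.6% instead of 5%. The detectable rate is understated by a factor of 1.8.

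This assumes that participants are independent, share a common event probability, and are all observed for the event. Incomplete observation would make detection worse. How the 2.3% arose cannot be determined from the plan. The error is confined to the safety-detection statement; the primary and responder analyses are untouched.

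**What to change.** Replace the sentence in Section 7.3 with wording to this effect:

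> If 70 participants are treated, the probability of observing at least one unexpected serious device-related event is 95% when its true incidence is 4.2% or more, and about 80% when it is 2.3%.

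State the formula, 1 − (1 − p)^n, beside it. In the report, recompute the figure for the number actually treated and give it next to the confidence intervals planned in Section 7.11.

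In the same edit, settle whether 70 is a maximum or a minimum, since Section 7.3 uses both descriptions.

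The cost is one sentence and a less favourable figure, with no extra participants and no change to the design. If the sponsor wants to keep both 95% and 2.3%, the study would need 129 treated participants, 59 more than planned.

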7.4 Timing of Analysis

The primary evaluation phase of the study lasts until all participants have reached the primary endpoint at 13-weeks (3-month) postprocedure. The primary and secondary endpoints will be analyzed using the data from the primary evaluation phase for an interim study report when these data become available. Informational outcomes will be analyzed and may be included in interim reports after all participants have reached each of the successive follow-up time points. A final study report will be provided after all participants have reached the final 36-month follow-up evaluation of the extended follow-up phase of the study.

7.5 Analysis Populations

All enrolled participants entered in the study will comprise the safety population and will be subject to all safety analyses. All enrolled participants undergoing the procedure (initiation of anesthesia) represent the evaluable study population. For some evaluations, summaries will be presented by nostril. The per-protocol population is defined as all participants who received treatment, with 13-week (3-month) follow-up data and no major protocol deviations.

7.6 Missing Data

Every effort will be made to obtain complete follow-up data for all participants, and it is anticipated that analysis of the primary and secondary endpoint hypotheses will be conducted using all available complete data. The effect of missing data will be examined by imputing missing NOSE scores as no change from baseline and as nonresponders.

Other outcome measures will be analyzed by using available data only.

7.7 Pooling

All study data will be pooled across study sites to facilitate hypothesis testing in accordance with the sample size estimation and power analysis (Section 7.3). Comparability between study sites may be shown using summary statistics calculated by site.

7.8 Participant Disposition

A detailed description of participant disposition will be provided using a CONSORT diagram and summaries of participants falling in various subgroups of interest, such as, consented but not treated, discontinued, major protocol deviations, deaths, and withdrawals. All study population exclusions and reasons will be summarized. All participants entered in the study will be accounted for in the summary. Follow-up by visit will be presented, showing theoretical, expected, and actual follow-up visits.

7.9 Demographics and Baseline Characteristics

Demographics and baseline characteristics will be summarized using frequencies and percentages for categorical factors and mean, median, SD, minimum and maximum for continuous factors.

7.10 Primary Endpoint Analysis

The primary endpoint hypothesis of change from baseline to the 13-week endpoint will be analyzed using a paired t-test at the 1-sided alpha .025 level and presented as the mean change with associated 1-sided lower confidence bound.

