5.5.2 Study Success

The study will be considered a success if the mean improvement in NOSE Scale score from baseline (screening) to 13 weeks exceeds 25 points.

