7.11 Secondary Endpoint Analysis

The secondary endpoint hypothesis will be tested only after the primary endpoint of the study is met. The secondary hypothesis will be evaluated using the proportion of responders on the primary outcome measure at 13 weeks. A responder is defined as having improvement in NOSE Scale score of $\geq 20\%$ from baseline or at least one NOSE Scale class improvement.

The hypothesis will be tested at the 1-sided alpha .025 level with a single proportion binomial test. The responder proportion (percent) will be presented with the associated 95% confidence interval. The secondary endpoint will be met if the lower bound of the confidence interval exceeds 0.55 (55%).

The frequency (proportion) of septal perforation will be calculated along with the 95% confidence interval along with a summary of each event.

Clinical Study Protocol – SWELL Study

The frequency (proportions) of serious device-related adverse events and procedure-related adverse events will be calculated along with the 95% confidence interval along with a summary of each serious event.

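### The primary result is reported with the confidence bound on the wrong side, and neither study success nor the gate to the secondary test is tied to the one-sided 0.025 test against -25

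*Combined protocol and SAP*

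**What the plan says.** Section 7.2 sets the primary hypothesis on the change in NOSE score, calculated as "13-week NOSE Scale score – baseline NOSE Scale score", and adds: "Note that improvement is represented by a decrease in NOSE score". The null is a mean change of -25 or higher and the alternative is a mean change below -25. Section 7.3 repeats this pair of hypotheses with one-sided alpha 0.025.

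Under Section 7.10 the primary hypothesis "will be analyzed using a paired t-test at the 1-sided alpha .025 level" and the result is "presented as the mean change with associated 1-sided lower confidence bound". No confidence level is given for that bound.

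Section 5.5.2, under the heading for success and failure criteria, reads: "The study will be considered a success if the mean improvement in NOSE Scale score from baseline (screening) to 13 weeks exceeds 25 points". It names no test, alpha level or bound.

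Section 7.11 begins: "The secondary endpoint hypothesis will be tested only after the primary endpoint of the study is met". It does not say what meeting the primary endpoint requires. For the secondary endpoint the same section is explicit: the lower confidence limit of the responder proportion must exceed 0.55.

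**The concern.** There are two separate wording faults around a valid test.

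The first is the side of the bound. A claim that a mean lies below -25 is supported when its upper confidence bound lies below -25. The lower bound of the change shows how large the improvement might be, not whether it exceeds 25 points. As written, the figure printed beside the primary result does not answer the primary question.

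The second is the decision rule. Taken at face value, Section 5.5.2 compares the observed mean with 25 and makes no allowance for sampling error. That is a different and much weaker rule than the t-test. Because Section 7.11 does not say which rule opens the secondary test, the same ambiguity reaches the gate. Study success, and possibly the secondary test, could then be claimed on data for which the prespecified test fails. In a single-arm open-label study the comparison with 25 points is the whole confirmatory claim on the primary endpoint, so the rule should be unambiguous.

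**Working it through.** **Inputs.** From Section 7.3: n = 70, SD of change 20, expected change -50, null value -25, one-sided alpha 0.025. From Section 7.2: change is 13-week minus baseline.

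**The plan's power.** SE = 20/√70 = 2.390. Noncentrality = (50 − 25)/2.390 = 10.46. The critical value t(0.975, 69) is 1.995. Power from the noncentral t distribution is above 0.9999, consistent with the stated 0.99, which 14 participants would already reach. The test is correctly set and amply powered at the planned effect.

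**Side of the bound.** Half-width = 1.995 × 2.390 = 4.77. At an observed change of -50:

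- lower bound: -50 − 4.77 = -54.77 (what Section 7.10 asks for)
- upper bound: -50 + 4.77 = -45.23 (what matches the alternative)

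If someone took a lower bound below -25 as the criterion, it would pass at any observed mean below -25 + 4.77 = -20.23, with probability 0.975 when the true change is exactly -25. The plan does not set that rule; this only shows that the lower bound carries no evidence for the claim.

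**Observed improvement needed.** The t-test rejects when the observed improvement exceeds 25 + 4.77 = 29.77 points. Section 5.5.2 read literally needs just over 25. The two disagree between 25.0 and about 29.8. For SDs other than the plan's 20 (assumed values) the test threshold is 28.58 at SD 15 and 30.96 at SD 25. The documents give no dropout rate; if 10% were missing (n = 63, an assumption), it is 30.04 at SD 20.

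**An example inside the gap.** Observed improvement 27.0: t = (27 − 25)/2.390 = 0.837, one-sided p = 0.20, upper bound of the change = -27 + 4.77 = -22.23. The null is not rejected, yet Section 5.5.2 is satisfied.

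**Chance of success** (n = 70, SD 20). The literal rule uses the normal probability Φ((true improvement − 25)/2.390); the test uses the noncentral t distribution.

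| True mean improvement | Literal 5.5.2 | t-test |
|---|---|---|
| 25 | 50% | 2.5% |
| 27 | 80% | 13% |
| 30 | 98% | 54% |
| 35 | >99.9% | 98.5% |
| 50 (planned) | about 100% | about 100% |

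A simulation with 100,000 runs at each of 25, 27 and 30 points agreed: 0.497 against 0.024, 0.800 against 0.127, and 0.983 against 0.542.

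**The case against.** Section 5.5.2 nearly repeats the hypothesis as phrased in the Protocol Summary and Section 7.2, where it plainly concerns the population mean. Section 7.2 speaks of rejecting the null, Section 7.3 powers the study to do so, and Section 7.10 names the test. On that reading, meeting the primary endpoint means rejecting the null, the plan's error rate is 2.5%, and the 50% figure describes a rule nobody intended. The planned 50 points also lies more than 8 standard errors above the top of the disputed range: (50 − 29.77)/2.390 = 8.5.

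On the bound, the lower side would be right if the result were expressed as improvement, so this may be a slip of one word. The interval is symmetric, so a reader who has the mean and one bound can recover the other at the same confidence level. The test and its p-value are untouched.

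Much of this stands. The test is valid, the success probabilities for Section 5.5.2 are conditional on a literal reading, and the rules agree at the planned effect. But Section 7.10 says change, which Section 7.2 defines with the opposite sign, and nothing in the plan corrects it; that a reader could work out the right bound does not make the reported one right. Section 5.5.2 is presented as a success criterion, beside a participant-level criterion in Section 5.5.1 that is applied to observed scores, so the literal reading is a fair one. Section 7.11 defines success by a bound for the secondary endpoint only. Section 7.2 does not settle the matter either: it describes rejection as evidence of a significant reduction from baseline without mentioning the 25-point margin.

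**Conclusion.** The concern holds and should be fixed. On the plan's own sign convention, Section 7.10 names the wrong bound; this is a reporting error that leaves the test intact. Sections 5.5.2 and 7.11 do not tie success, or the opening of the secondary test, to that test. If Section 5.5.2 is applied literally, it and the t-test give opposite verdicts for observed improvements of about 25.0 to 29.8 points, and the chance of declaring success at a true improvement of exactly 25 points is 50% rather than 2.5%. These figures assume the plan's n = 70 and SD 20; the upper end of the range moves only between about 28.6 and 31.0 for SDs of 15 to 25. The consequence is confined to a true effect well below the planned 50 points, which is why this is a wording correction and not a fault in the design.

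**What to change.** Change three sections.

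- **Section 7.10:** state that the mean change (13-week minus baseline) is tested by paired t-test against a null value of -25 at one-sided alpha 0.025, and reported with its one-sided 97.5% upper confidence bound or a two-sided 95% interval. Equivalently, report the mean improvement (baseline minus 13-week) with its lower 97.5% bound. Either the sign or the side must change, not both.
- **Section 5.5.2:** define study success as rejection of the Section 7.2 null at one-sided 0.025, that is, an upper 97.5% bound of the mean change below -25.
- **Section 7.11:** state that the secondary hypothesis is tested only if the primary endpoint is met, defined as rejection of the Section 7.2 null at one-sided 0.025.

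The cost is wording only. Sample size does not change and power at the planned -50 stays above 0.99. No new hurdle is added: Section 5.5.2 is aligned with the bar that Sections 7.2, 7.3 and 7.10 already set.
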